#### 5.7.6 Intention-to-treat analyses of primary outcome

We will also report intention-to-treat analyses including:

- all children, who had a home visit by a study nurse (i.e., including children who did not receive assigned treatment, children who were not enrolled because they were moribund, or who did not accept to participate).

#### 5.7.7 Sensitivity analyses

In sensitivity analyses, we will assess whether the conclusions are robust to censoring at general health intervention campaigns, and whether we can identify if OPV and BCG prevents cause-specific hospitalisations or deaths (for details, see appendix: analysis plan).

## 6 TIME SCHEDULE AND ECONOMY

The trial will be initiated with a pilot study in Biombo in June 2015. The trial will be scaled up to full study including Oio and Cacheu regions in July 2016. The trial will be expanded to include the urban study area in July 2017. We expect enrolments to end in December 2020. External funding will be sought, but the Research Center for Vitamins and Vaccines, Bandim Health Project and Statens Serum Institut guarantee to cover the project finances.

## **7 DISSEMINATION OF RESULTS**

The findings will be published in international peer-reviewed journals and results with implications for WHO vaccination policy implementation will be communicated to WHO's Strategic Advisory Group of Experts on Immunization (SAGE) and Global Advisory Committee on Vaccine Safety. A report of the study results will be provided to the National Institute of Public Health. The close cooperation between BHP and the Ministry of Health in Guinea-Bissau will ensure that the information gathered will be disseminated to the national primary health programme.

## **8 ETHICAL CONSIDERATIONS**

BCG is recommended at birth but vaccination is often delayed; in rural Guinea-Bissau most children receive BCG when aged >1month. While there may now be increasing acceptance that BCG has beneficial non-specific effects, we are still a long way from altering the implementation of the vaccination programme. The proposal compares two ways of delivering BCG and both will be an improvement relative to the current situation, where less than 40% of all infants get BCG during the first month of life. Hence, no child will receive BCG later than it would have done, had the trial not been carried out.

### **8.1 Explanation to participants**

The pregnant women will receive an oral and a written explanation of the study at the time of registration. It will be explained that normally new-born children should go to the closest health centre to receive their first vaccinations. However, some studies have suggested that it might be beneficial to receive BCG and OPV early and the BHP will therefore like to know whether it is worthwhile to provide the vaccination at home. The study will therefore give BCG+OPV to children in half of the clusters. The study will therefore provide standard care in control clusters and standard care and vaccines in intervention clusters. It will be explained that children in the control clusters can seek vaccination elsewhere and will be offered the BCG vaccine and OPV at the next home visit.

### **8.2 Informed consent**

All pregnant women will receive an oral and a written explanation of the study, and be offered to participate in the study at the time of registration of the pregnancy. In the rural area the explanation will be given by the BHP nurse at the two-monthly visits. In the urban area the explanation will be given by the fieldwork assistant at a monthly visit. If the pregnant woman accepts to take part in the study, they will be asked to sign or fingerprint a consent form. The fingerprint has to be confirmed by an independent witness who also signs the form. At the home visit after birth, the study nurse will explain the study to the mother again and ask for oral confirmation of consent to participate in

the study. If the mother is not able to present the signed consent form, new consent forms will be filled out.

### **8.3 Safety monitoring**

WHO recommends the BCG and OPV vaccines to be given at birth in low-income countries. The safety of the BCG Japan vaccine, which is used for the present study, have been evaluated by WHO, who has approved the vaccine. OPV is provided from the national health programme. Adverse reactions are rare for both BCG and OPV. At the two first visits after enrolment in the study, the BHP nurse will examine the BCG vaccination site and the axillary lymph glands of all children to assess suppurative lymphadenitis as an adverse reaction to the BCG vaccination. Other serious adverse events will be captured through primary and/or secondary outcomes (mortality, hospitalisations and consultations).

A data safety and monitoring board will oversee the trial procedures.

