## 5.4 Procedures

### 5.4.1 Enrolment

The study nurse will visit every new-born child shortly after a CKI calls, if possible on the same day. At the home visit immediately after birth, the nurse will ask the mother of the child for confirmation of her consent for participation in the study before revealing the randomisation (for details see section 8.1). The nurse will bring a questionnaire, a study number, sticker with study number and a vaccination card.

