### 5.4.3 Follow-up

All children enrolled in the study will receive two follow-up visits, and will be followed to 4 months of age.

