### 5.7 Statistical analyses

All children registered during pregnancy will enter the study when they are visited at home or 24 hours after birth, whichever comes last, thereby excluding deaths and hospital admissions on the day of birth.

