Appendix 2 - Planned analyses

1 Baseline

Descriptive statistics:

For eligible children visited by a study nurse within 72 hours after birth, we will describe reasons for exclusion by group allocation.

Distribution of background factors will be presented by group allocation overall and by sex and region. Background factors will be summarised by counts (percentages), means (standard deviation) or medians (interquartile range) as appropriate. Information on the proportion with missing information will be provided.

Table 1: Summary of background factors by intervention and control group

• Sex• Age at enrolment• Region• Weight at enrolment• Temperature• Mid-upper-arm circumference• Head circumference• Place of birth• Socioeconomic factors (maternal education and housing conditions)

2 Primary analysis of primary outcome

The primary analysis of early infant non-accidental mortality will be assessed on a per-protocol (PP) analysis allowing for different baseline hazards according to factors used in the randomization (Region, pre-study mortality level (high/low)) and sex, thus allowing different baseline hazards for boys and girls. To account for clustering we will employ cluster-robust variance estimates.

For the primary outcome, we will use Cox proportional hazards models that allow different baseline hazards according to the above mentioned factors and with age as underlying time-scale. Deaths due to accidents will be censored.

The primary analysis of the primary outcome is described in more detail in table 2.

Table 2: Primary analysis of primary outcome

Population	Children visited within 72 hours after birth are eligible for the study. Exclusion criteria:
------------	---

	
 - Children already BCG vaccinated - Moribund children (Expected not to survive the next 24 hours, as evaluated by the health facility nurse at the enrolment visit) - Children in rural villages where the BHP mobile teams coincidentally were in the village the same day (and vaccinated all children)
Observation period	
From: Enrolment visit or 24 hours after birth, whichever comes last
 
To: 60 days of life
 
Censoring, first of:
 
 - Visit by the BHP - 60 days - Death due to accident - Date of registering first non-trial vaccine given after enrolment - Migration (migration out of the study area as per HDSS definition)
Time scale	Age
Failure definition	Death

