Growth measures	Weight will be analysed using the WHO weight-for-age z-score
Statistical tool	Linear regression
Adjustment	We will adjust the analysis for weight-for-age at enrolment, sex, region and pre-study mortality level
Clustering	We will use robust standard errors to account for clustering within village cluster

Stata code	Regress w-z-score random w-z-enrol sex b1.reg prmorlev, vce(cl regam) *w-z-score=weight-for-age z-score at first visit by the mobile teams, w-z-enrol=weight-for-age z-score at enrolment, reg=region, prmorlev=pre-study mortality level, regam=village cluster
------------	---

BCG scarring

Table 12: BCG scarring

Population	Identical to primary analysis of primary outcome
Observation timepoint	First visit after 6 months of age
Failure definition	Scar (yes/no)
Statistical tool	Log-binominal regression
Adjustment	We will adjust the analysis for sex, region and pre-study mortality level
Clustering	We will use robust standard errors to account for clustering within village cluster
Stata code	Binreg scar random sex b1.reg prmorlev, rr vce(cl regam) *reg=region, prmorlev=pre-study mortality level, regam=village cluster

Cost-effectiveness of providing BCG and OPV at birth

A cost effectiveness analysis seeking to measure the cost per death averted using a societal perspective will be performed, contrasting the costs of vaccine provision in the present programme and an outreach system as tested in the trial. The costs/savings associated with different rates of consultations and admissions will also be taken into account.

Suppurative lymphadenitis

We will assess the incidence of suppurative lymphadenitis as a reaction to BCG vaccination in the intervention and control clusters. Other serious adverse events to the BCG and OPV vaccine will be captured through the outcome measures (mortality, hospital admission and consultations).

5 Sensitivity analyses to test for robustness of conclusions

Table 13: Cause-specific death

Population	Identical to primary analysis of primary outcome
Observation period	From: Enrolment visit or 24 hours after birth, whichever comes last To: 60 days of life Censoring, first of:

	
 - Visit by the BHP - 60 days - Death due to accident - Date of registering first non-trial vaccine given after enrolment - Migration (migration out of the study area as per HDSS definition)
Time scale	Age

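### Apart from lymphadenitis, serious adverse events are reported only through the efficacy window, so events before 24 hours of age in infants vaccinated that early, and events after the window closes, enter no planned safety analysis

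*Protocol*

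**What the plan says.** Protocol 8.3 describes one dedicated safety assessment: the vaccination site and axillary glands are examined at the first two visits after enrolment, to detect suppurative lymphadenitis. It then says: "Other serious adverse events will be captured through primary and/or secondary outcomes", naming mortality, hospitalisations and consultations. SAP Appendix 2, section 4, compares lymphadenitis incidence between arms and adds: "Other serious adverse events to the BCG and OPV vaccine will be captured through the outcome measures".

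The observation period for those outcomes is set elsewhere. Protocol 5.7 has children enter at the home visit or 24 hours after birth, "whichever comes last, thereby excluding deaths and hospital admissions on the day of birth". SAP Table 2 has the same rule, "From: Enrolment visit or 24 hours after birth, whichever comes last", and Tables 7, 8 and 9 repeat it. All four tables end observation no later than day 60, and earlier at a BHP visit, a first non-trial vaccine or migration.

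Two other sections bear on this. Protocol 5.4.1 on timing of the visit: "The study nurse will visit every new-born child shortly after a CKI calls, if possible on the same day". Protocol 5.4.3 on length of follow-up: "All children enrolled in the study will receive two follow-up visits, and will be followed to 4 months of age".

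**The concern.** The window was built for an efficacy question. Late entry removes events tied to the birth itself, and stopping at the first follow-up visit is sensible because control children are then offered BCG. Neither reason applies to a safety summary. Safety is normally counted from the moment of exposure and for as long as children are observed, whatever later happens to the contrast between arms.

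Because the plan has no other route for serious events, the safety summary inherits both limits. An infant vaccinated at 5 hours of age who dies at 18 hours would appear in no outcome. A death or admission recorded at the second follow-up visit would be in the database but in no safety result.

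Protocol 1.2 reports a mortality effect of BCG within three days of vaccination, so the plan itself treats the first days as biologically informative. Protocol 7 intends to send policy-relevant findings to a global vaccine-safety committee. That audience will ask about the first hours and about the whole follow-up period.

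**Working it through.** The plan states no figure for this point, so there is nothing to reproduce. The check compares windows and then does simple person-time arithmetic.

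**1. Windows of the outcomes that carry serious adverse events**

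| SAP table | Outcome | Start | Ends at the first of |
|---|---|---|---|
| 2 | Non-accidental death | Later of enrolment visit and 24 h after birth | BHP visit, non-trial vaccine, migration, day 60, accidental death |
| 7 | Non-accidental admission | Same | The first four above, death, accident admission |
| 8 | Death or admission | Same | The first four above, accidental death or admission |
| 9 | Consultation | Same | The first four above, death, end of study |

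The outline code for Tables 2, 7 and 8 enters children at the later of date of birth plus 1 and date of enrolment, so it works in calendar dates.

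**2. Does any other analysis reopen the window?** SAP section 5 lists cause-specific death (same window, Table 13), censoring at campaigns, the intention-to-treat population, all-cause mortality and repeat admissions. These change the cause, population, censoring or event count. None states an earlier start or a later end. Protocol 5.7.6 changes only the population.

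**3. Early gap.** For an infant vaccinated at age h hours, the time from vaccination to entry is max(24 − h, 0).
- h = 5: 24 − 5 = 19 hours outside the window.
- h of 24 or more: 0 hours. Nothing is lost at the start.
- As a share of the first 72 hours after vaccination, the loss is at most 24/72 = 1/3. At h = 5 it is 19/72 = 26%.

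**4. Late gap.** Take 4 months as 120 days.
- Days 61-120 are outside for every child: 60/120 = 50%.
- For an infant vaccinated on the day of birth, the longest possible window is day 1 to day 60: 59/120 = 49% inside and 51% outside.
- A BHP visit, a non-trial vaccine or migration before day 60 shortens the window further.

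**5. Are the late data collected?** Yes, for deaths and admissions. Protocol 5.4.3.1 and 5.4.3.2 record vital status and admissions during routine follow-up, 5.5.2 asks about admissions at the follow-up visits, and protocol Table 1 schedules a morbidity and mortality interview at the second and third routine visits as well as the first. No analysis in either document uses the later data for safety.

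**6. Contrast with lymphadenitis.** It is examined at two visits, and its analysis has no stated day-60 or first-visit cut. The plan already looks past the first visit for one safety event.

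**The case against.** The best counter-argument is that capture means collection. Protocol 8.3 is a monitoring section. It points to outcomes that protocol 5.5 defines without a 24-hour delay: mortality there runs from the home visit, and admissions have no day-60 limit. The late entry and day-60 stop are analysis rules. This stands in part: the gap is in analysis and reporting, and it would be wrong to say later events go unrecorded. It does not remove the point, because the SAP ties serious events to the outcome measures and gives no analysis of those measures outside the window.

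Several stronger readings are tempting and should not be drawn.
- *Safety rests on the efficacy outcomes alone.* Lymphadenitis is assessed separately.
- *Every event to 4 months is lost.* Events inside the window are counted.
- *About three quarters of rural safety information is lost.* If first visits were uniform over days 0-60, the mean window would be about 29 days and 1 − 29/120 = 76% of person-time would lie outside. The visit distribution is not given, and person-time is not events. Protocol section 2 puts about 75% of neonatal deaths in the first week, and much of the omitted time follows the offer of BCG to controls.
- *Some 1000 to 2000 infants are affected early.* That needs an assumed 30-60% of 3333 (6666/2) vaccinated on the day of birth. The documents give no such share, and the same-day target runs from the informant's call, not from birth.
- *The trial would wrongly declare safety to 4 months.* Neither document plans that statement.

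It is also fair that both vaccines are recommended at birth, that the BCG product is WHO-approved and that a data safety and monitoring board exists. The board's stated remit is to oversee procedures; no event listing or reporting rule is described.

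**Conclusion.** The point holds as a reporting gap with two parts. The early part affects only infants vaccinated before 24 hours of age. It removes up to the first 24 hours after vaccination, and its frequency cannot be derived from the documents. The late part affects every child: at least 60 of 120 days of planned follow-up lie outside, given 4 months taken as 120 days. That is a share of time, not of events.

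The entry and stopping rules are the same in both arms, and this point is no criticism of the efficacy window. No primary estimate or conclusion changes. It is a worthwhile, inexpensive improvement: without it, the stated capture rule leaves out the earliest post-vaccination events and all events after the window closes.

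**What to change.** Leave Tables 2 and 7-9 as they are. In protocol 8.3 and SAP Appendix 2, section 4, add a descriptive safety table by arm.

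- **Population:** all children who had a study-nurse visit.
- **Events:** all-cause deaths, overnight admissions and consultations.
- **Period:** from the date of the visit to the 4-month follow-up, with no 24-hour delayed entry and no stop at the first BHP visit.
- **Bands, in calendar days since the visit:** day of visit; days 1-3; day 4 to first follow-up visit; first follow-up visit to 4 months. Use hours only if clock times of birth, visit and event are recorded; the documents do not show that they are.
- **Label:** after the first follow-up visit, state that the arms compare early with later BCG.
- **Recipient:** give the same table to the data safety and monitoring board.

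The cost is wording in two places and one table. Deaths and admissions are already collected at visits that take place anyway. Consultations are not named in the protocol's list of routine follow-up items, so confirm that the morbidity interview at later visits records them. The downside is that the earliest row will include birth-related events and must be read against the control arm.

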### **8.4 Potential problems**

In case of vaccine shortage of BCG Japan, the study group will consult the Data Safety and Monitoring Board to discuss, whether the study should be discontinued or if the study can proceed with another BCG vaccine.

## **9 IMPLICATIONS**

WHO recommends BCG at birth for normal-birth-weight children. However, due to the focus on not wasting vaccine doses BCG vaccination is delayed in many low-income countries. WHO recommends three home visits after birth, which is resource demanding and not implemented in many low-income countries. It is not recommended that the home visits are utilised for early vaccination. If we can confirm our hypothesis of reduced early infant mortality by providing BCG and OPV at a single home visit, this should be included in the WHO recommendations, and it will be an incentive for countries to introduce a single home visit with vaccines. In countries, where home visits are already in place, vaccines can easily be added to reduce early infant mortality.

**Table 1: Trial design**

Timing	Routine visit before birth	Shortly after birth – within 72 hours		1st routine visit after birth	2nd and 3rd routine visit after birth
Personel	BHP Field assistant (FA) and Nurse	Community Key Informant (CKI)	Study Nurse	BHP FA and Nurse	BHP FA and Nurse
Control group	Information about trial and invitation to participate. Informed consent.	CKI inform about birth	
 
• Umbilical cord and skin care
 
• Encourage skin-to-skin contact to keep the new-born warm
 
• Examine and Weigh the child
 
• Inform about vaccination opportunities
 
	FA: 
 
• Interview on morbidity and mortality
 
 Nurse: 
 
• Examine the BCG vaccination site and lymph glands
 
• Measure temperature
 
• Weigh the child
 
• Provide BCG and OPV
 
	FA: 
 
• Interview on morbidity and mortality
 
 Nurse: 
 
• Examine the BCG vaccination site and lymph glands
 
• Measure temperature
 
• Weigh the child
 
• Provide routine vaccinations
 

Intervention group			
 
• Umbilical cord and skin care
 
• Encourage skin-to-skin contact to keep the new-born warm
 
• Examine and weigh the child
 
• Administer BCG and OPV
 
	FA: 
 
• Interview on morbidity and mortality
 
 Nurse: 
 
• Examine the BCG vaccination site and lymph glands
 
• Measure temperature
 
• Weigh the child
 

Appendix 1: General analysis principles

1 Participant population

All main analyses will be completed in a per-protocol (PP) population of all BCG-unvaccinated children, who received a home visit within 72 hours after birth, and who received the assigned treatment. The primary analysis and hence the main conclusion of the trial will be based on the PP analysis. Unless explicitly stated all analyses will be PP.

Since the cluster-size varies, data will be analysed on individual level data. All statistical tests will be 2-tailed and $p \leq 0.05$ considered statistically significant for analyses involving the primary outcome.

2 Unadjusted and adjusted analyses

Both unadjusted analyses and analyses adjusted for place of delivery will be reported. Conclusions will be based on the unadjusted analyses.

3 Multiple testing

P-values will not be corrected for multiple testing. Secondary outcomes are tested to observe if the pattern is similar across other health outcomes. Consequently, $p \leq 0.05$ will not be employed as a threshold for statistical significance for secondary outcomes. For the sensitivity analyses, we will not consider statistical significance, but rather robustness of the conclusions across different definitions of outcomes and co-variates.

4 Missing data

All analyses will be complete-case analyses.

5 Proportional hazards

To test the proportional hazards assumption, a required assumption of the Cox regression, we will perform formal significance tests based on Schoenfeld residuals. In addition, we will assess proportionality by allowing the hazard ratio to interact with the underlying timescale to identify a possible time trend. Finally, we will assess proportionality graphically via log-log survival curves.

Significance tests based on Schoenfeld residuals will be performed via the stata command *estat phtest, detail* leading to both a global test and a test for each covariate, the latter being relevant only when we study effect modifications. Presentation of log-log survival curves will be undertaken via *stphplot*. Finally, possible interactions between hazard ratios and the underlying time scale will be

further investigated via the *stcox* procedure and the *tvc()* option. For the models including effect modifications we will construct a new interaction variable (i.e., a four-level variable representing the interaction) such that a graphical assessment of proportionality can be undertaken assessing the four-level variable in a log-log survival plot.

If we identify evidence for non-proportionality, we will still report the marginal hazard ratios but supplement this measure by hazard ratios for 2-3 properly selected categorical time-periods identified based on the aforementioned proportionality investigations.

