## 5.2 Study design and randomisation

We will conduct a cluster-randomised trial, randomising clusters to two different treatment groups, stratified by region and pre-trial mortality level (high/low). Pre-trial mortality level is assessed using the BHP rural HDSS data from 2012 to 2015. Pre-trial mortality level in the urban area will be based on the BHP urban HDSS data from 2013 to 2016, to account for a change in the registration system in 2012.

Randomisation of clusters will be by computer generated random numbers. All new-borns will be visited as soon as possible after birth. To children in half of the clusters we will provide standard care and vaccines (BCG, OPV) at the home visits; children in the remaining clusters will only receive standard care but no vaccines (Table 1).

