### 5.4.2 Intervention

For all children, the nurse will examine and weigh the child, encourage skin-to-skin contact to keep the new-born warm and if necessary perform umbilical cord care. For children in the control clusters, the nurse will inform about vaccination opportunities (vaccination at closest health centre or vaccination by BHP nurse at next visit), as recommended by WHO. For children in the intervention clusters, the nurse will inform the parents that it is recommended to administer BCG and OPV at birth. If parents accept vaccination, the nurse will administer BCG and OPV, opening a vial of BCG even if there is just one child to be vaccinated (Table 1). Children in the intervention group will be vaccinated with BCG and OPV within 72 hours after birth.

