### 5.4.5 Exclusion criteria

There are very few exclusion criteria, because the study is expected to answer a pragmatic question about the effect of BCG and OPV vaccination at home visits shortly after birth.

- Children born outside the cluster, and returning more than 72 hours after the delivery
- Children that the nurse evaluates to die within the next 24 hours.

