#### 5.7.3 Primary analysis of the primary outcome

In the primary analysis of the primary outcome, we will compare the effect of BCG and OPV on early infant mortality in a Cox proportional hazards model with age as underlying time. The analysis will be performed on a per-protocol population consisting of all BCG-unvaccinated children visited within 72 hours after birth, who received the assigned treatment. Follow-up will be censored at:

- Subsequent visit by the BHP in rural areas or follow-up visits by the study nurse in the urban area, where children in the control group will receive BCG
- Date of registration of first non-trial vaccine
- Death due to accident
- Migration

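### The primary per-protocol set requires receipt of the assigned treatment, which in practice drops unvaccinated children from the intervention arm only

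*SAP*

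**What the plan says.** SAP Appendix 1, section 1, defines the main population as BCG-unvaccinated children who had a home visit within 72 hours "and who received the assigned treatment", and adds: "The primary analysis and hence the main conclusion of the trial will be based on the PP analysis". Protocol 5.7.3 gives the same population, "consisting of all BCG-unvaccinated children visited within 72 hours after birth, who received the assigned treatment".

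What counts as assigned treatment differs by arm. Under protocol 5.2, "children in the remaining clusters will only receive standard care but no vaccines". In intervention clusters, protocol 5.4.2 says: "If parents accept vaccination, the nurse will administer BCG and OPV". Consent to the trial is confirmed earlier, "before revealing the randomisation" (protocol 5.4.1), so accepting the vaccine is a separate, later step that exists in one arm only.

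An intention-to-treat analysis is planned. Protocol 5.7.6 gives it as an additional report. SAP Appendix 2, section 5, files it among the sensitivity analyses, which Appendix 1, section 3, says are read for robustness and not for significance.

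SAP Table 2, the detailed specification of the primary analysis, lists three exclusions: already BCG-vaccinated, moribund, and same-day presence of the mobile team. Non-receipt of the assigned treatment is not among them, although the text before the table calls the analysis per-protocol.

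**The concern.** The condition reads the same for both arms but acts on one. A control child left unvaccinated at the visit has received the assignment. An intervention child left unvaccinated has not, and is removed after the arm is known. The control children whose parents would have declined the vaccine cannot be recognised, so they remain.

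If the children removed carry higher mortality than those kept, the intervention arm looks better with no vaccine effect at all. If they carry lower mortality, a real benefit is understated. The trial seeks to show a 40% mortality reduction (protocol section 4), and protocol 5.4.5 keeps exclusions few "because the study is expected to answer a pragmatic question". The analysis that carries the conclusion should therefore compare children by cluster allocation.

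**Working it through.** **Which child stays in the primary set**

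- Control, not vaccinated at the visit: stays (protocol 5.2).
- Intervention, vaccinated: stays.
- Intervention, not vaccinated: removed (protocol 5.4.2 with 5.7.3 and SAP Appendix 1, section 1).
- Control, vaccinated at the visit by mistake: removed, but this child is not unvaccinated.

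**Size of the bias under no vaccine effect**

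Let x be the share of intervention children not vaccinated and r their hazard relative to vaccinated children in the same arm. Both are assumptions. Set the vaccinated children's hazard to 1. The control arm, which keeps everyone, has average hazard (1 − x) + x·r, so

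HR = 1 / (1 − x + x·r).

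Example: x = 5%, r = 3 gives 1 / (0.95 + 0.15) = 0.91.

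| x | r = 0.5 | r = 1 | r = 3 | r = 5 |
|---|---|---|---|---|
| 1% | 1.005 | 1.00 | 0.98 | 0.96 |
| 2% | 1.01 | 1.00 | 0.96 | 0.93 |
| 5% | 1.03 | 1.00 | 0.91 | 0.83 |
| 10% | 1.05 | 1.00 | 0.83 | 0.71 |

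Against the target HR of 0.6, x = 5% uses up ln 0.909 / ln 0.6 = 19% of the hypothesised log hazard ratio at r = 3, and ln 0.833 / ln 0.6 = 36% at r = 5.

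**Effect on the false-positive rate**

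Inputs from protocol 5.3: 6666 children, 2.4% with the composite event, design effect 1.35. With x = 5% and r = 3:

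- control events: 3333 × 0.024 = 80.0
- intervention events: 80.0 × 0.95 × 0.909 = 69.1
- SE = √[1.35 × (1/80.0 + 1/69.1)] = 0.191
- shift: ln 0.909 / 0.191 = −0.50

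The two-sided 5% test then rejects 7.9% of the time. At r = 3 the rate is 5.1% for x = 1%, 5.5% for x = 2% and 15.1% for x = 10%. These figures are for the composite. The documents give no event proportion for mortality alone; fewer events would leave the HR bias unchanged and reduce the inflation.

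**Cost of analysing by allocation**

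First, the plan's own sample size. Schoenfeld's formula gives 4 × (1.960 + 0.842)² / (ln 0.6)² = 120.3 events; × 1.35 = 162.4; / 0.024 = 6768, which is 1.5% above 6666. This reads 2.4% as the overall proportion and uses the two-sided test of SAP Appendix 1. A one-sided 5% test with 2.4% as the control proportion (mean of arms 1.92%) gives 94.8 × 1.35 / 0.0192 = 6664, so the plan's own derivation is not certain. Both readings of the 2.4% are shown below, with a two-sided test.

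With a true HR of 0.6 in vaccinated children and non-receivers at average risk (r = 1), the diluted HR is 0.6(1 − x) + x.

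| x | HR | Power, 2.4% overall | Power, 2.4% in controls | N for 80% (2.4% overall) |
|---|---|---|---|---|
| 0 | 0.600 | 79.4% | 70.1% | 6768 |
| 2% | 0.608 | 77.3% | 68.0% | 7133 |
| 5% | 0.620 | 74.0% | 64.9% | 7728 |
| 10% | 0.640 | 68.1% | 59.5% | 8867 |

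If non-receivers are frailer, dilution is greater. At x = 5% and r = 3 the HR is (0.95 × 0.6 + 0.05 × 3) / (0.95 + 0.05 × 3) = 0.655.

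**The case against.** Several points on the other side stand.

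- Nothing shows that the bias is large. The documents give neither x nor r; at 1% to 2% non-receipt with r = 3 the effect is small, and it could run the other way.
- A reader might infer that nurses will pass over sick infants. The documents do not say so. Parental acceptance is the only stated condition for vaccination, a vial is opened even for one child, and moribund children are excluded in both arms. Selection on health is plausible: protocol 1.2 notes that BCG is often delayed in low-birth-weight children, and SAP Table 5 calls birthweight an important mortality risk factor. It remains an inference.
- A reader might infer that randomisation is undone. That is too strong. Cluster allocation is untouched; what weakens is the comparability of the children analysed, to an unknown degree.
- An intention-to-treat analysis is planned, with its own section in the protocol, and SAP Appendix 2, section 1, will describe reasons for exclusion by arm.

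The last point does not remove the problem. The planned intention-to-treat analysis does not carry the conclusion, and it also brings in moribund children and those who declined to participate. A difference from the per-protocol result could not then be put down to non-receipt. No planned analysis takes consenting, eligible children by allocation alone. Describing exclusions gives transparency, not an unbiased estimate.

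It can also be said that the sponsor wants the effect of the vaccines as received. The per-protocol contrast estimates that only if non-receipt is unrelated to risk, which the plan neither argues nor examines.

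**Conclusion.** The point holds. The condition on which the main conclusion rests removes, in practice, unvaccinated children from the intervention arm only, after the arm is known. That one-arm effect follows from protocol 5.2, 5.4.1 and 5.4.2 read together; it is not stated outright.

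The size rests wholly on assumed x and r. The bias is negligible near 1% non-receipt, modest at 2%, and material at 5% to 10% if non-receivers are clearly frailer. It is absent at r = 1 and reversed below that. The documents do not support a claim that the result will favour the intervention, only that the plan leaves it open to a bias of unknown size and direction which it could avoid.

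Separately, and whatever x and r turn out to be, SAP Table 2 conflicts with SAP Appendix 1, section 1, and protocol 5.7.3. An analyst working from the table alone would keep children whom the other two texts remove.

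**What to change.** - Delete the receipt condition ("and who received the assigned treatment" in SAP Appendix 1, section 1, and the matching clause in protocol 5.7.3) from the primary population.
- Relabel the population in the SAP text before Table 2 so that it is no longer called per-protocol. The exclusions listed in Table 2 can stand.
- Analyse all consenting, eligible children visited within 72 hours by cluster allocation, whatever they received, and base the conclusion on that analysis.
- Keep the present per-protocol set as a sensitivity analysis.
- Report the number of children left unvaccinated in intervention clusters, and their mortality.

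The change should be fixed before results by arm are seen. It needs wording only and no new data. The price is dilution: with non-receivers at average risk, two-sided power at 6666 children (composite, 2.4% as the overall proportion) falls from about 79% to 77% at 2% non-receipt, 74% at 5% and 68% at 10%. The loss is small where non-receipt is rare. Where non-receipt is common the loss is real, but that is also where the present set is most exposed to bias.
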